## 2. Colleagues do not obtain subjects' consent for the research or act as representatives of the investigators

### Specify 'Other' recruitment methods:

The coordinator will prescreen patients and introduce the study in person. The surgical team will also assist with identifying potential eligible subjects. When possible, the coordinator will then attend the pre-surgical appointment to fully consent the patient. Occasionally, pre-surgical appointments are telemedicine appointments where the coordinator may not be available and introduce the study over the phone and email the consent form if patients wish to review the consent form. The coordinator will obtain full consent on the day of surgery. Please note that even if the patient has previously consented, the coordinator will confirm their continued consent on the day of surgery.

### Specify the precautions taken to avoid compromised objectivity:

## Informed Consent Process

Does this study involve the creation, use, or disclosure of **Protected Health Information (PHI)**?  
Yes

### Methods of [Health Insurance Portability and Accountability Act \(HIPAA\)](#) Authorization

Identify the HIPAA authorization process (**Check all that apply**):

Partial waiver of HIPAA authorization for screening/recruitment purposes only. Signed authorization obtained prior to further access to PHI

---

### Methods of [Informed Consent](#)

Identify the consent or assent process as applicable for each participant population (**check all that apply**):

Paper-based signed informed consent/assent

#### **Paper-based Signed Informed Consent**

Indicate the paper-based signed informed consent/assent (**check all that apply**):

Signed Informed Consent

**REQUIRED!** Submit the Adult Consent Form, Child [Assent Form](#) and/or Parental Permission Form in the Attachments Section.

---

### Circumstances of Consent

Indicate the location where the consent process will take place (**check all that apply**):

Over the phone

Private room

Specify how the research team will assure that subjects, their parents, or their legally authorized representative (LAR) have sufficient time to consider whether to participate in the research:

Subjects or their LAR will be allowed to take home the unsigned consent form for review prior to signing it

---

This study does NOT include [Non-English Speaking Participants](#). Scientific justification/rationale is required in the Eligibility Criteria Section for Subject Populations.

## Waiver of HIPAA Authorization

### You requested a Partial Waiver of HIPAA Authorization

When a partial waiver is requested, the Lead Researcher is requesting the HIPAA research authorization be waived for a portion of the study, such as a waiver for subject identification or recruitment purposes.

Please specify for what purpose the partial waiver is requested:

Partial waiver of HIPAA authorization requested for screening/recruitment purposes only. Signed authorization obtained prior to further access to PHI.

### Justification for a Waiver of HIPAA Authorization

Does the use or disclosure of personal health information involve more than minimal risk?

No

Would the granting of the waiver adversely affect privacy rights and welfare of the individuals whose records will be used or disclosed?

No

Explain (justify) the answer:

The use of personal health information (PHI) in this study involves minimal risk, as it is limited to screening and recruitment purposes. Identifiable information will only be accessed by the research team and will be de-identified before further use. Privacy protections, including the destruction or anonymization of personal identifiers, will be implemented once the data is no longer needed. Therefore, granting the waiver will not adversely affect the privacy rights or welfare of the individuals, as appropriate safeguards will be in place.

Could the research practicably be conducted without a waiver of HIPAA authorization?

No

Explain the answer:

The research cannot be practically conducted without a waiver of HIPAA authorization because accessing personal health information (PHI) is essential for identifying and recruiting eligible participants. The study relies on reviewing PHI, such as patient names and contact information, to determine whether individuals meet the eligibility criteria for the study. Without this information, the research team would not be able to approach potential subjects or effectively recruit participants. Therefore, a waiver is critical to ensure the study can proceed as planned, particularly during the initial phase of recruitment.

Could the research practicably be conducted without access to, use or disclosure of the personal identifiers listed in the PHI question?

No

Explain the answer:

The research relies on personal identifiers, such as patient names and contact information, to identify and screen potential participants who meet the study's eligibility criteria. These identifiers are essential for reaching out to eligible individuals and recruiting them into the study. Without access to this information, the research team would be unable to efficiently select participants, making it impractical to conduct the study. Therefore, access to personal identifiers is necessary for the study to proceed as planned.

Are the privacy risks reasonable relative to the anticipated benefits of the research?

Yes

Describe the risk/benefit analysis performed to explain the answer above:

The privacy risks in this study are considered minimal because personal health information (PHI) will only be used for screening and recruitment, and strict safeguards will be in place. Only the research team will have

access to identifiable information, and any PHI will be de-identified or destroyed once no longer needed. The study will not involve sensitive data that could significantly impact participants' privacy if disclosed. The anticipated benefits, such as advancing scientific understanding and potentially improving patient care, justify the minimal risks to privacy. Given the protections in place, the risk of improper disclosure is low, and the potential benefits to the participants and the broader medical community make the risks reasonable.

Describe the plan to protect the personal identifiers from improper use and disclosure (i.e., describe data security methods):

Personal identifiers will be protected through a combination of physical, technical, and administrative safeguards. Data will be stored in secure, password-protected electronic systems with restricted access, ensuring only authorized research team members can view or use the information. Physical records containing personal identifiers will be kept in locked, secure locations. Any data transmitted electronically will be encrypted to prevent unauthorized access. Additionally, personal identifiers will be removed or de-identified as soon as they are no longer necessary for the study. These measures will ensure that personal identifiers are

safeguarded from improper use and disclosure throughout the research process.

Describe the plan to destroy the personal identifiers at the earliest opportunity, or provide a health or research justification for retaining the identifiers:

Personal identifiers will be destroyed or anonymized as soon as they are no longer necessary for the study. If a participant decides not to continue in the study, any identifying information will be promptly removed from the data and securely destroyed. For participants who consent to continue, personal identifiers will be retained only as long as needed for study procedures, such as tracking surgery dates or patient outcomes. Once the data collection phase is complete or identifiers are no longer required for analysis, all personal identifiers will be securely destroyed or de-identified. This approach ensures that personal information is retained only for the

minimum time necessary to achieve the research objectives and is disposed of in accordance with HIPAA guidelines.

Describe how potential subjects will be identified:

Potential subjects will be identified by reviewing the surgical schedule for patients undergoing posterior spinal fusion surgery at UCI Medical Center. The research team will cross-reference the schedule with the study's inclusion and exclusion criteria. Eligible patients must be 18 years or older, undergoing posterior spinal fusion surgery, and willing to sign the consent and HIPAA forms. Patients who meet the inclusion criteria and do not have any of the exclusion criteria (such as allergies to opiates, chronic pain unrelated to the surgery, psychiatric illness, substance abuse history, BMI over 35, pregnancy, or inability to provide informed consent) will be approached during their preoperative consultation. The research team will explain the study, address any questions, and obtain written consent from those who are interested in participating.

## Research Procedures

Check all boxes that apply to the research:

Analysis of Existing Identifiable or Coded Data, Specimens, Records, Charts, and Datasets

Clinical Investigation involving on Investigational Drug or Biological Product (including the on or off label use of an FDA approved drug)

Surveys/Questionnaires/Interviews/Oral Histories

## Clinical Phase of Study

Indicate the phase(s) of the study, if applicable:

N/A

Will deception or incomplete disclosure be involved in the research?

with deception or incomplete disclosure be involved in the research?

No

### Study Design

Include an explanation of the study design (e.g., randomized placebo-controlled, cross-over, cross-sectional, longitudinal, etc.) and, if appropriate, describe stratification/randomization/blinding scheme:

This is a prospective, randomized, double-blinded study. The surgical team will screen for and identify potential patients undergoing posterior spinal fusion surgery using the UCI Medical Center surgical schedule. If the subject is deemed ineligible based on the inclusion and exclusion criteria after reviewing their medical history, his/her record will be discarded. If a subject is deemed eligible, information regarding their next visit prior to their surgery will be relayed to the research team. A member of the study team will speak with patients during their preoperative consultation in a private room and review the details of the study with them. The patient may choose to have their relatives in the room during this consent process. The patient will be enrolled in the study only after one of the investigators reviews the consent form with the patient, ensuring the patient

understands the study, answers all questions, and written informed consent is obtained. Subjects will be informed that their participation is voluntary and will not impact their patient care. The subject's privacy will be protected. Only the information relevant to study will be obtained.

Occasionally, patients are approved for surgery via a telehealth visit or during an otherwise standard clinical visit. The study team will review the surgical schedule and screen for potential patients. As these surgeries are often scheduled 3-4 weeks after they are cleared for surgery, the study team will call to introduce the study and email the consent documents at minimum 48 hours prior to surgery but typically the patient will have those 3-4 weeks to review the consent document and ask questions. The study team will obtain full written informed consent on the day of surgery, in their private room within the pre-op area. The details of the study will be re-reviewed to ensure the patient fully understands. The subject's information will be kept confidential; if data is written on paper, the paper will be either

kept in the research folder, which is kept in the hospital or shredded when it is not needed. If subject data is kept on a computer, the data will only be stored on hospital computers. Subject information will not be shared beyond the IRB approved research team as listed in Section 2 of this protocol narrative. Once consented, the subjects will be randomized by the study team into one of the three study groups: (1) low dose remifentanyl, (2) high dose remifentanyl combined with ultra-low dose naloxone or (3) high dose remifentanyl combined with placebo. The randomization list will be prepared before the study starts using a random number table generator and the study coordinator will obtain the information for each subject after consent. Personnel directly involved in subject care will be blinded as to naloxone or placebo administration. The pain assessors (second blinded group) will be blinded. Surgical procedures will not be altered and subjects will still receive standard subject care. Following consent, a packet of questionnaires (includes baseline questionnaire, Public Health Questionnaire (PHQ-9), VAS, McGill Short Form, Brief Pain Inventory) will be provided to subjects by study staff. All subjects will be required to complete a baseline questionnaire to obtain subject demographics prior to surgery. Opioid-induced hyperalgesia OIH will be measured by determining experimentally induced pain thresholds and clinically meaningful outcomes of pain via validated pain questionnaires and post-operative opioid consumption. These outcomes have previously been used and validated to assess remifentanyl-induced hyperalgesia; pain thresholds to cold and static mechanical stimulation are the most common pain modalities altered by remifentanyl infusion. Experimentally induced pain will be performed in pre-op by quantitative sensory testing via von Frey filaments applied in ascending order to the dorsal surface of the subject's non-dominant hand and 5cm from the incision site. Subjects will be instructed to indicate when stimulus produces a painful sensation as well as when the stimulus becomes unpleasant. In addition to determination of mechanical pain thresholds, cold pain threshold and tolerance will be determined. Subjects will be instructed to immerse their hand in a bucket of ice water and indicate when they first experience a painful sensation (threshold) and to remove their hand from the ice water when they can no

longer tolerate the pain (tolerance). The time for pain tolerance and threshold will be recorded. Validated pain questionnaires will be administered to subjects prior to surgery and 48h after cessation of remifentanyl infusion. These questionnaires will include the McGill Short Form pain questionnaire and the Brief Pain Inventory (short form). The McGill questionnaire provides an assessment of pain quality and descriptors, whereas the Brief Pain Inventory assesses both pain intensity and pain unpleasantness (the emotional component of pain is considered to be a better metric of subject satisfaction and quality of life). A research assistant blind to treatment will administer both experimentally induced pain assessments and pain questionnaires before surgery and after the surgery. As part of the study, subject demographics (age, gender, surgery type) and hemodynamics (heart rate, blood pressure, etc) that are obtained as standard operating room procedure will be accessed. Measures will be taken to protect subject privacy by only allowing IRB approved research personnel to access records as needed. The table below indicates the timing and outcome measures that will be determined.

	Pre-op Consult	Post-surgery	4h	8h	12h	24h	48h	PHQ-9	VAS	McGill Pain Questionnaire	UCI IRB Approved: 08-26-2021   MOD# 29836
Baseline History	x										
Brief Pain Inventory		x									
Von Frey Testing		x	x	x							
Cold Pressor Test		x	x	x							
Opioid Consumption		x	x	x	x	x					

Statistical Considerations 1. Statistical Analysis Plan: Describe the statistical method(s) for the stated specific aims and hypotheses described in Section 1. Note: Required for scientific review. 2. Explain how the overall target sample size was determined (Provide power / sample size justification for the study). If a statistical analysis plan is not appropriate for your study design, please describe a plan for assessing your study results. Statistical Analysis Plan For the primary outcome, the 2-sample t-test will be applied to compare the difference in mechanical pain thresholds at 24 and 48h between HN and HI group, and between LO and HI group. For the secondary outcomes, the continuous variables will also be analyzed using 2-sample t-test to identify the difference between HN and HI group, and between LO and HI group. The mean level and corresponding 95% confidence interval (CI) will be obtained for each study

group. The categorical outcomes will be analyzed 1 Pre-op Consult  
 Subjects screened for inclusion/exclusion criteria Study introduction  
 during surgical consult visit Subjects provided with consent form and study  
 information sheet 2 Lab Visit Initiate subject consent Hamilton Rating  
 Scale, VAS, McGill Pain Questionnaire, Brief Pain Inventory Finalize Consent  
 3 Pre-Surgery Subject is greeted in preop area Von Frey Testing, Cold  
 Pressor Test, Opioid Consumption Pre-surgery medication: standard-of-  
 care 4 Surgery Group 1 (LO): Induction dose per anesthesiologist (no  
 ketamine); Maintenance: 0.1mcg Remifentanyl Group 2 (HI): Induction dose  
 per anesthesiologist (no ketamine); Maintenance: 0.4mg Remifentanyl +  
 Saline Group 3 (HN): Induction dose per anesthesiologist (no ketamine);  
 Maintenance: 0.4mg Remifentanyl + 0.004mcg/kg/min Naloxone 5 Post-  
 Surgery Post-surgery medication: standard-of-care @4H, @8H, @ 12H: VAS,  
 Opioid Consumption @24H: VAS, Von Frey Testing, Cold Pressor Test,  
 Opioid Consumption @48H: Hamilton, VAS, McGill, Brief Pain Inventory,  
 Von Frey, Cold Pressor, Opioid Consumption UCI IRB

Provide precise definitions of the study endpoints and criteria for evaluation; if the primary outcomes are derived from several measurements (i.e., composite variables) or if endpoints are based composite variables, then describe precisely how the composite variables are derived:

see above

### **Statistical Considerations**

Is a statistical analysis plan appropriate for this qualitative study design?

Yes

Describe the statistical methods for the stated specific aims and hypotheses. Your analysis plans should match the stated study specific aims and hypotheses:

For the primary outcome, the 2-sample t-test will be applied to compare the difference in mechanical pain thresholds at 24 and 48h between HN and HI group, and between LO and HI group. For the secondary outcomes, the continuous variables will also be analyzed using 2-sample t-test to identify the difference between HN and HI group, and between LO and HI group. The mean level and corresponding 95% confidence interval (CI) will be

obtained for each study group. The categorical outcomes will be analyzed using the chi-square test and the odds ratio (compare to HI group) and corresponding 95% CI will also be obtained.

Describe the statistical method(s) that will be used to analyze the primary outcome(s) or endpoints:

see above

If appropriate describe secondary or post hoc analyses of primary outcome(s) or other exploratory analysis and if necessary, provide a breakdown of the methods used per outcome or endpoint:

Secondary outcomes: - Opioid consumption required to control pain over the first 24 and 48h post-operatively. - Cold pressure test for pain threshold and pain tolerance - VAS pain scores measured prior to surgery and at 4, 8 and 12h after extubation and again at 24h and 48h post-operatively. - McGill short form questionnaire to be filled out prior to surgery and at 48h post-operatively - Brief Pain Inventory questionnaire to be filled out prior to surgery and at 48h post-operatively

**Sample Size Determination:** Explain how the overall target sample size was determined (e.g., power analysis; precision estimation), providing justification of the effect size for the primary outcome based on preliminary data, current knowledge/literature and/or cost consideration; if appropriate, provide sample size justification for secondary outcomes. Power analysis should (at least) match the primary outcome/endpoint:

The sample size determination and power analysis was based on a 2-sided 2-sample t-test with a significant level of 0.05. The following table shows the minimum effect size to detect for various sample size and power. We propose to recruit a total of 105 subjects (35 per group) and expect to have 96 subjects (account for 8% attrition) for final analysis. The proposed sample size will provide the study 80% power to detect an effect size of 0.71 and 90% power to detect an effect size of 0.82.

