Attempts have been made with various agents to reduce the development of tolerance and hyperalgesia following remifentanil. Postoperative hyperalgesia and its prevention has been studied with ketamine[10, 11, 15-36], Magnesium [12, 34, 37], Gabapentin[16], Clonidine[19, 38], Lornoxicam [18], Dextromethorphan [39], Paracetamol [40, 41], Morphine [42], Dexmedetomidine [43], Adenosine [44, 45], COX inhibitors [46, 47], Amantadine [48], Nitrous oxide [49], Fentanyl [50], Pregabalin [51], Buprenorphine [52], Midazolam [53], Dexamethasone [36]. Relevant to our current hypothesis is the report that concomitant administration of ultra-low dose naloxone [13] and naltrexone [54] with remifentanil prevented OIH. However, there are no studies on reducing the adverse effects of remifentanil with ultra-low dose naloxone in human subjects. While the traditional role of opiate antagonists have been in cases of opioid overmedication, recent evidence is emerging regarding their use in pain management. Gan et al. 1997 used an ultra-low dose naloxone infusion (0.00025 mg/kg/h or 0.001 mg/kg/h) in postoperative patients receiving IV morphine via a patient-controlled analgesia (PCA) device. Good pain relief was experienced in all groups, however consumption of PCA morphine was significantly reduced in patients that received the lowest infusion of naloxone and opioid-induced side effects (nausea, vomiting, pruritus) were reduced by naloxone at both dose.

Describe the primary outcome variable(s), secondary outcome variables, and predictors and/or comparison groups as appropriate for the stated study objectives/specific aims:

The primary outcome variable of the study will be to determine the occurrence of OIH in high dose remifentanyl treatment group compared to a low dose Remifentanyl group and a high dose Remifentanyl dose with ultralow dose naloxone. OIH will be determined by assessing evoked pain thresholds. Secondary outcomes will include verbal assessment of overall pain levels via validated standard pain questionnaires and post-operative opioid consumption to determine presence of opioid analgesic tolerance. The predicted outcome is that ultralow dose naloxone will attenuate the development of remifentanyl-induced OIH. Primary outcome: Mechanical pain threshold, determined by von Frey filaments, around the incision site at 24 and 48h post-surgery. Primary hypothesis: The mechanical pain thresholds at 48h in the HN group is higher than in the HI group. Secondary

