hypotheses: 1. The mechanical pain thresholds at 48h in the LO group is higher than in the HI group. 2. The mechanical pain thresholds at 24h in both HN and LO group is higher than in the HI group. Secondary outcomes: - Opioid consumption required to control pain over the first 24 and 48h post-operatively. - Cold pressure test for pain threshold and pain tolerance - VAS pain scores measured prior to surgery and at 4, 8 and 12h after extubation and again at 24h and 48h post-operatively. - McGill short form questionnaire to be filled out prior to surgery and at 48h post-operatively - Brief Pain Inventory questionnaire to be filled out prior to surgery and at 48h post-operatively Other data collected will include a baseline history questionnaire (for demographics, age, sex, weight, income level) and the Public Health Questionnaire (PHQ-9) to measure depression as mood greatly influences pain perception. The PHQ-9 will be used to determine whether groups have been stratified appropriately.

List up to ten relevant references/articles to support the rationale for the research:

1. Bekhit, M.H., Opioid-induced hyperalgesia and tolerance. *Am J Ther*, 2010. 17(5): p. 498- 510. 2. Lin, S.L., et al., Co-administration of ultra-low dose naloxone attenuates morphine tolerance in rats via attenuation of

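### Pre-operative values are collected for the primary outcome and most secondary outcomes, but every continuous outcome is compared by an unadjusted t-test, which gives up precision the data could supply.

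*Combined protocol and SAP*

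**What the plan says.** Background & Purpose of the Research defines the primary outcome as "Mechanical pain threshold, determined by von Frey filaments, around the incision site at 24 and 48h post-surgery". The primary hypothesis concerns the post-operative level: "The mechanical pain thresholds at 48h in the HN group is higher than in the HI group".

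Study Design provides a baseline for that outcome: "Experimentally induced pain will be performed in pre-op by quantitative sensory testing via von Frey filaments applied in ascending order", on the back of the non-dominant hand and 5 cm from the incision site. The visit flow at the end of that section places von Frey and cold pressor testing in the pre-surgery step and again at 24h and 48h. VAS, McGill and Brief Pain Inventory are also completed before surgery.

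Statistical Considerations, repeating text in Study Design, gives one method: "For the primary outcome, the 2-sample t-test will be applied to compare the difference in mechanical pain thresholds". It is used at both post-operative times, with HI as the comparator for HN and for LO. Secondary outcomes follow suit: "For the secondary outcomes, the continuous variables will also be analyzed using 2-sample t-test". The sample size paragraph powers the same unadjusted test. No section mentions a covariate, a change score or a mixed model.

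**The concern.** When an outcome is measured before and after treatment, the part of the between-patient variation that the baseline predicts can be removed from the error term. A t-test on the post-operative value alone leaves it in. It also leaves any chance difference in starting threshold between arms in the point estimate. The interval allows for that difference on average but does not correct for it in the sample at hand. The baseline measurements cost staff time and patient discomfort, and the plan gives them no role in estimating the treatment effect. At stake is how wide the intervals are and how small an effect the planned 105 patients could have detected.

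**Working it through.** **Inputs.** From the sample size paragraph: two-sided alpha 0.05; 105 recruited, 35 per arm; 96 evaluable after 8% attrition (105 × 0.92 = 96.6), so 32 per arm; 80% power at 0.71 SD and 90% at 0.82 SD. The correlation r between the pre-operative and post-operative value is not in the documents and is varied from 0 to 0.7.

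**Step 1: reproduce the plan.** For a two-sample t-test the noncentrality is d × √(n/2) = d × √16 = 4d, with 62 degrees of freedom (df).
- d = 0.71: noncentrality 2.84, power 79.8%.
- d = 0.82: noncentrality 3.28, power 89.8%.

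The plan's figures are confirmed.

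**Step 2: adjust for baseline.** With one ANCOVA over three arms, the residual SD is SD × √(1 − r²). The noncentrality becomes 2.84 / √(1 − r²), with 96 − 4 = 92 df.

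| Assumed r | √(1 − r²) | Noncentrality at 0.71 SD | Power |
|---|---|---|---|
| t-test | – | 2.84 | 79.8% |
| 0 | 1.000 | 2.84 | 80.2% |
| 0.2 | 0.980 | 2.90 | 81.8% |
| 0.3 | 0.954 | 2.98 | 83.8% |
| 0.5 | 0.866 | 3.28 | 90.1% |
| 0.7 | 0.714 | 3.98 | 97.6% |

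The effect detectable with 80% power falls from 0.71 SD to 0.68, 0.61 and 0.51 at r = 0.3, 0.5 and 0.7. At r = 0.5 the adjustment is worth 32 / (1 − 0.25) = 43 patients per arm. The formula ignores the small cost of estimating the slope; a simulation that includes it gave 84%, 90% and 97% at r = 0.3, 0.5 and 0.7.

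**Step 3: how much comes from the third arm.** Pooling the residual variance over three arms without a covariate raises the df from 62 to 93 and power from 79.8% to about 80.3%. That is negligible, and it assumes equal variance in all arms. The gain comes from the baseline.

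**Step 4: would a change score do as well?** Its SD is SD × √(2(1 − r)). At 0.71 SD its power is 66% at r = 0.3 and 79.8% at r = 0.5. It beats the plain t-test only when r exceeds 0.5, and it is not a substitute for ANCOVA.

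**Step 5: the 8 patients enrolled.** The split between arms is not stated; assume 3/3/2. A 3-versus-3 t-test has 4 df. The three-arm ANCOVA has 8 − 4 = 4, because the third arm pays for the covariate. The simulated median half-width of the 95% CI for a 3-versus-3 contrast is about 2.1 SD unadjusted. Adjusted, it is about 2.2 SD at r = 0.3, 2.0 at r = 0.5 and 1.6 at r = 0.7.

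**The case against.** The t-test is a legitimate choice. Under randomisation it is unbiased, its type I error is correct, and the plan reaches its stated 80% power without adjustment. All of that stands, so this is a point about efficiency.

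The gain also depends on an unknown r. Baseline is taken on unoperated skin and the outcome near a fresh wound after opioids, so a weak correlation is possible. That stands too, which is why the table starts at r = 0. At the planned size, adjustment costs essentially nothing even there.

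It could be argued that comparing the difference in thresholds already means change from baseline. The sentence goes on to name the two groups being compared, the hypotheses concern post-operative levels, and no change score is defined, so this reading is not supported.

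Some readers might infer more than the documents support:
- **That ignoring baseline is a severe problem in the 8-patient data.** Step 5 does not bear this out: intervals are slightly wider with adjustment at r of 0.3 or below, about even at 0.5, and narrower at 0.7.
- **That PHQ-9 should become a covariate and its balance check be dropped.** The plan says "The PHQ-9 will be used to determine whether groups have been stratified appropriately", and no stratified randomisation is described. But the visit flow schedules the Hamilton scale and does not list PHQ-9, so it is unclear which instrument was collected. The balance check does no harm.
- **That pre-operative opioid use must be added as a covariate.** Nothing in the documents makes this necessary.

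**Conclusion.** The point holds as a loss of precision and of protection against chance imbalance. It is not bias, and it does not invalidate the planned test. For the planned design, power at 0.71 SD would move from 79.8% to between about 80% and 98% as r runs from 0 to 0.7. The size within that range is unknown because the documents give no correlation. The calculation also assumes a common residual variance and a linear relation with the same slope in each arm.

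The benefit belongs mainly to the 105-patient design. The trial closed with 8 enrolled, and for those data the effect on precision is mixed; a half-width of 1.6 to 2.2 SD is inconclusive either way. The analysis had not been run when the closure form was written, so the choice can still be fixed in advance.

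**What to change.** In Statistical Considerations, and in the duplicate text in Study Design, replace the t-tests with one ANCOVA over all three arms: post-operative value = arm + pre-operative value of the same measure. Report the HN−HI and LO−HI contrasts with 95% CIs. For the primary outcome, name the von Frey value taken 5 cm from the incision site as the covariate, since a hand value is also recorded. The Study Design text gives no distance for the post-operative test, so state that it uses the same location. Keep the unadjusted comparison for outcomes with no matching baseline.

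The cost is one model statement and no new data or visits. Because data collection is complete, the change also needs a documented, dated amendment before the pending analysis is run, so that the model cannot appear to have been chosen after seeing the results.
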